With regard to societal benefits, this study will provide data that may benefit patient populations that suffer from primary sleep disorders, as well as poor sleep due to neurologic and psychiatric illness. This study may indicate that home application of tACS during sleep is a practical and affordable treatment for patients. tACS is an inexpensive, noninvasive, and safe intervention, so providing data that supports its efficacy may substantiate its utility in reducing healthcare costs.

XIX. PROVISIONS TO MONITOR THE DATA FOR THE SAFETY OF PARTICIPANTS

Identification and documentation of adverse events will be the responsibility of the PIs and co-investigators, who will also be performing data collection. Reporting of adverse events will be the responsibility of the principal investigator, [name]. A review of summarized safety information will be performed by [name] and will occur after 1 subject has participated in the study as well as midway through data collection. The study will be stopped if any serious adverse event occurs. A statistical interim analysis will not be performed given that this study is minimal risk.

XX. PROVISIONS TO PROTECT THE PRIVACY INTERESTS OF PARTICIPANTS

All efforts will be made to protect the privacy of research subjects. However, since this study does not involve sensitive data, no privacy measures will be taken other than the data management steps outlined in section XIV.

XXI. MEDICAL CARE AND COMPENSATION FOR INJURY

Medical care and compensation for injury are not applicable given that this is a minimal risk study.

XXII. COST TO PARTICIPANTS

There are no costs to subjects.

XXIII. DRUG ADMINISTRATION

Not applicable.

XXIV. INVESTIGATIONAL DEVICES

The StarStim (<http://www.neuroelectrics.com>) stimulator qualifies as an investigational device. It will deliver the tACS to the patient. The device is battery powered and controlled by a microprocessor for

safety monitoring and to ensure precise current delivery. The device consists of a stimulator, a programmer, and EEG recorder and a set of electrodes. The device is programmed with safety features to limit current intensity, voltage, and impedance to assure stimulation is kept well below accepted safety guidelines, and has been designed to allow safe at-home use. There are no anticipated changes to the device during the course of this study. Starstim is considered a non-significant risk device, as defined under 21 C.F.R. § 812.3(m).

XXV. MULTI-SITE STUDIES

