Official Title: Application of Transcranial Alternating Current Stimulation for Modulation of Sleep and Cognitive Performance

NCT03112902

June 4th, 2019

TITLE: Application of transcranial alternating current stimulation for modulation of sleep and cognitive performance.

PROTOCOL VERSION DATE: 04June2019

COMIRB# 16-1875

PRINCIPAL INVESTIGATOR (PI):

Name: [name], PhD

Address: Department of Neurology

University of Colorado School of Medicine
[name]
[name]
[name]

[contact]

Email: [contact]

I. OBJECTIVES

Impaired sleep, in particular fragmented sleep and loss of slow wave activity (SWA) during non-rapid-eye-movement (NREM) sleep, is known to occur during the physiologic process of aging (1-3). Disrupted sleep is particularly pronounced among patients with diagnoses of Mild Cognitive Impairment (MCI) and those who progress to Alzheimer's Disease (AD), and is associated with worsening of cognitive impairment with progression of brain pathophysiology (4, 5). Recent advances in non-invasive neuromodulation via transcranial electric stimulation (tES) offer a chance for immediate impact on sleep and cognition, with a safe and readily available technology (6, 7). Neurophysiologic mechanisms of tES have been elucidated in both animal and human brains, and include local changes in cortical excitability (8, 9) and synaptic plasticity (10), with global modulation of cortical networks and functional connectivity (11, 12). Transcranial alternating current stimulation (tACS), a type of tES, has been demonstrated to modulate sleep architecture and cognitive performance when applied during SWA (7, 13). *Thus, we propose that application of tACS has the potential to improve sleep quality among patients with MCI, and to additionally improve measures of cognitive performance, mood, and quality of life.*

Hypotheses and Specific Aims: The purpose of this research is to investigate the utility of transcranial alternating current stimulation (tACS) to modulate sleep, cognition, mood, and quality of life among normal healthy adults, older adults, as well as individuals with mild cognitive impairment (MCI). We will do this with the following Specific Aims:

- 1). Optimize tACS parameters for duration, intensity and frequencies via utilization of EEG data recorded during tACS stimulation.
- 2). Determine whether recording artifacts introduced by tACS can confidently be removed from EEG signals.

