- 3). Determine effects of tACS delivered with nested frequencies(multi-frequency signal) vs single frequency tACS, with regard to intrinsic EEG signal, for modulation of SWA coherence and power, as recorded in our overnight EEG sleep data.
- 4). Determine the cumulative effects of tACS delivered in multiple, consecutive nights on underlying EEG signals, sleep architecture, sleep quality and cognitive function among patients with MCI.

5). Determine if tACS is a viable treatment for disturbances of sleep and cognitive performance among patients with MCI.

6). Generate pilot data and manuscripts to support applications for larger randomized placebo-controlled clinical trials.

We hypothesize that through multiple and consecutive sessions, there are cumulative effects of tACS on sleep architecture, with subsequent impacts on cognitive performance, mood and quality of life among normal health adults, older adults, as well as individuals with MCI.

II. BACKGROUND AND SIGNIFICANCE

Transcranial alternating current stimulation (tACS) is a form of transcranial electrical stimulation (tES), similar to transcranial direct current stimulation (tDCS), each of which utilizes scalp electrodes to deliver current at low amperage through brain cortex. In the case of tACS this current is set to alternate in a specific frequency (14). This transcranial current flow has been demonstrated to alter cellular membrane potentials, with subsequent alteration of cortical excitability and synaptic potentiation (10). The use of tES in human trials has increased markedly within the last 15 years, and to date hundreds of trials with thousands of subjects have been reported without any serious side effects (10, 15). The benefits of tES have been demonstrated in treating the cognitive symptoms of many neurological illnesses including Alzheimer's disease, Parkinson's disease, stroke, depression and epilepsy; notably with exceptional tolerability and without any major safety concerns reported (16-22).

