Sleep impairment is common among patients with MCI and AD, and has been associated with worsening cognitive function and progression of the neurodegenerative process (reviewed in (29)). The pathological process of A β and tau accumulation has been associated with disruption of normal sleep physiology (4, 30, 31), and has been more specifically linked with the loss of SWA during NREM that is the hallmark of disease progression in MCI and AD (32). The process of memory consolidation occurs during SWA, and the loss of SWA in the context of disrupted sleep physiology has been demonstrated to produce symptoms of cognitive impairment (3, 32, 33). Further, a causal relationship between disruption of sleep and progression of neurodegenerative process has been demonstrated in animal models of AD (34, 35), and it has been suggested that a bi-directional relationship exists between sleep disruption and worsening AD pathology, with one of the functions of sleep being to clear toxic compounds from the brain (reviewed in (36)). Thus, targeted interventions to improve sleep physiology offer opportunities for clinical intervention, which may not only treat symptoms of cognitive impairment, but may also slow or reverse the progression of neurodegeneration from MCI to AD.

Our objectives are to assess the effects of tACS on sleep architecture in EEG recording, as well as effects on sleep quality and cognitive function, for the purpose of developing large scale, randomized, placebo-controlled clinical trials. We propose that this technology is fundamentally safe, and relatively cost effective. Demonstration of successful tACS pilot studies will allow for development of subsequent studies with broad application to studies of brain and sleep neurophysiology, as well as to more rapid

development of therapeutics for treatment of patients with neurodegenerative disease including MCI and AD and potentially neuroprotective trials.

III. PRELIMINARY STUDIES

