Inclusion Criteria- The subject population will be individuals between the ages of 51-85 who are native English speakers. We will further require older adult subjects to enroll in the study with a study partner to help them with the technological aspects of applying equipment and performing home-based cognitive assessments.

Exclusion Criteria-

- brain tumors
- skull defects
- epilepsy
- metal implants/devices above the neck
- eczema or sensitive skin
- severe insomnia that limits ability to sleep at night
- currently taking sedatives and/or sleeping medications
- sleep apnea that requires CPAP
- REM-sleep behavior disorder
- currently pregnant or trying to become pregnant during the study period
- diagnosis of cognitive impairment.

MCI subjects:

Inclusion Criteria- The subject population will be individuals between the ages of 45-90 who meet clinical criteria for diagnosis of amnestic MCI and are native English speakers. We will further require MCI patients enroll in the study with a study partner to help them with technological aspects of applying equipment and performing home-based cognitive assessments.

Exclusion Criteria-

- brain tumors
- skull defects
- epilepsy
- metal implants/devices above the neck
- eczema or sensitive skin
- severe insomnia that limits ability to sleep at night
- currently taking sedatives and/or sleeping medications
- sleep apnea that requires CPAP
- REM-sleep behavior disorder
- currently pregnant or trying to become pregnant during the study period

VII. VULNERABLE POPULATIONS

MCI individuals are considered a vulnerable population due to their cognitive impairment. They are the subject of this research study, and thus MCI individuals must be included. Subjects with diagnosis of MCI will be screened for decisional capacity via the UCSD Brief Assessment of Capacity to Consent (UBACC), and subjects who are found to have impaired capacity will require a legally authorized representative for consent (40).

VIII. RECRUITMENT METHODS

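### The sleep part of Aim 5 asks about treating disturbed sleep in MCI, but the MCI branch neither requires disturbed sleep nor schedules a measure of it before treatment

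*Protocol*

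**What the plan says.** Protocol section I, Specific Aim 5, is to "Determine if tACS is a viable treatment for disturbances of sleep and cognitive performance among patients with MCI". This has two parts, sleep and cognition.

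Protocol section VI, MCI subjects, defines the population as "individuals between the ages of 45-90 who meet clinical criteria for diagnosis of amnestic MCI and are native English speakers", with a study partner. It sets no PSQI cut-off, diary criterion, sleep complaint or slow-wave threshold. The exclusions include "severe insomnia that limits ability to sleep at night", "currently taking sedatives and/or sleeping medications", "sleep apnea that requires CPAP" and REM-sleep behavior disorder.

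Protocol section II gives the premise, "Sleep impairment is common among patients with MCI and AD", without a prevalence. Section I describes disrupted sleep as especially marked in MCI, and names fragmented sleep and loss of slow wave activity as the features of interest.

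Protocol section IV.5 makes 0.5-2 Hz EEG power around each stimulation train the primary outcome. The Consensus Sleep Diary, the PSQI and sleep durations are secondary. The MCI tables in section XII.5 list the diary (after each study night), HADS, CGIC and the two memory tasks. They do not list the PSQI, and they list no adaptation or baseline night, although the older-adult branch has one.

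The SAP plans repeated-measures ANOVA for the primary and secondary outcomes. It names no covariate or subgroup for baseline sleep.

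**The concern.** A claim that something treats disturbed sleep needs either subjects known to have disturbed sleep or a record of who had it. As scheduled, the MCI branch has neither on the subjective side. The first diary entry follows the first study night, so it is not a pre-treatment measure.

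Two readings of the results are at stake. If a sleep measure improves, the result describes people with amnestic MCI whatever their sleep, minus the excluded groups. Protocol section II itself reports that tACS enhanced slow wave sleep in healthy adults, so a rise in slow wave power does not by itself show that a disturbance was corrected. If the PSQI, diary or sleep-duration outcomes show nothing, one explanation is that many subjects slept well enough to have little room to improve. Without a baseline measure, that explanation could be neither supported nor ruled out.

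**Working it through.** **Does the enrolled population match the question?**

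- Cognitive part: Aim 5 asks about disturbed cognitive performance, and section VI requires amnestic MCI. These match.
- Sleep part: Aim 5 asks about disturbed sleep. Section VI has no matching entry criterion, and four exclusions remove defined sleep-related groups. These do not match.
- Baseline record: section IV.5 names the PSQI, but the initial-visit, home and later-visit tables in XII.5 omit it. The diary comes after each night. The one sleep-related quantity available before any stimulation is the 0.5-2 Hz EEG power recorded before the first train on the first night.
- Analysis: the SAP has no baseline-sleep term.

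**The plan's own sample size.** Section IV.5 gives 30 subjects, 1:1, for a rise of at least 20% over sham, power 0.80, p < 0.05. No SD is given, so 30 cannot be reproduced from its inputs. With 15 per arm and a two-sided t-test at 0.05 (sidedness is my assumption), 80% power corresponds to:

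- degrees of freedom 28, critical t = 2.048
- noncentrality d × √(15/2) = 2.902, so d = 2.902 / 2.739 = 1.06
- implied SD for a 20-point effect: 20 / 1.06 = about 19 percentage points

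**Illustration of dilution.** Let q be the share of enrolled subjects with disturbed sleep, and r the response of normal sleepers relative to disturbed sleepers. With the SD held fixed, the average effect is d_eff = 1.06 × [q + r(1 − q)]. Power follows from the noncentral t with noncentrality d_eff × √(15/2) and 28 degrees of freedom. Both q and r are assumptions.

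| q (assumed) | d_eff, r = 0 | Power, r = 0 | d_eff, r = 0.5 | Power, r = 0.5 |
|---|---|---|---|---|
| 100% | 1.06 | 80% | 1.06 | 80% |
| 90% | 0.95 | 71% | 1.01 | 76% |
| 80% | 0.85 | 61% | 0.95 | 71% |
| 70% | 0.74 | 50% | 0.90 | 66% |
| 50% | 0.53 | 29% | 0.79 | 56% |
| 40% | 0.42 | 20% | 0.74 | 50% |

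Example: at q = 0.5 and r = 0.5 the multiplier is 0.5 + 0.5 × 0.5 = 0.75, so d_eff = 0.75 × 1.06 = 0.79 and power is 56%.

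The 80% starting point is a reference effect, not a promise in the plan. The 30 subjects were sized for EEG power, and the documents state no power for the secondary sleep outcomes.

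**The case against.** The strongest reply is that the protocol's disturbance is not a sleep complaint. It stresses fragmented sleep and loss of slow wave activity, calls the latter a hallmark of progression in MCI and AD, does not exclude it, and makes slow wave power the primary outcome. On that view, requiring amnestic MCI largely selects the disturbance. This stands in part: a reader might infer that the branch shuts out those with the worst sleep, but that holds only for severe insomnia and the listed conditions, not for low slow wave activity. It does not remove the point. No slow-wave deficit is required or defined either, and a group tendency does not characterise about 30 individuals.

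The exclusions also have a rationale. Section XII delivers stimulation only in stable stage 2 or deeper NREM sleep, which a person with severe insomnia may seldom reach. That stands; the exclusions are not contested here.

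The dilution figures at r = 0 assume that normal sleepers do not respond at all. That sits badly with section II, which reports benefit in healthy adults, and with branch 3, which is sized for a gain of at least 20% in healthy 18-50 year olds. This stands, and is why the r = 0.5 column is shown.

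Finally, Aim 6 and the background present the work as pilot data, and the SAP states no conclusion about treating sleep disturbance. That lowers the stakes. Aim 5 nevertheless poses a treatment question, and a pilot meant to support larger trials is more useful if the subjects' baseline sleep is known.

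**Conclusion.** The point holds for the sleep part of Aim 5. Disturbed sleep is not an entry requirement, no sleep-severity measure is scheduled before treatment, and no baseline-sleep covariate is planned. A positive result would be evidence of an effect on sleep measures in amnestic MCI unselected for sleep complaint and without the listed exclusions. A null on the secondary sleep outcomes would be ambiguous for disturbed sleepers.

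A reader might go further and infer that neither a positive nor a null result could answer Aim 5. The documents do not support that. The cognitive part is matched by the amnestic MCI requirement and by the memory tasks, and a positive sleep result would still be relevant evidence in the group enrolled.

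The size is uncertain. For an effect of d = 1.06, power is 71% to 20% over assumed shares of 90% to 40% if only disturbed sleepers respond, and 76% to 50% if normal sleepers respond half as much. These ranges rest on a two-sided t-test, 15 per arm, an unchanged SD, and values of q and r that the documents do not give. They show how ambiguous a null could be; they do not estimate the trial's power.

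**What to change.** 1. Restate the sleep part of Aim 5, and any conclusion drawn from it, as the effect on sleep measures in amnestic MCI unselected for sleep disturbance and without the listed exclusions. Leave the cognitive part as it is.
2. Add the PSQI, already a named outcome, to the MCI initial visit before randomisation, and report it by arm.
3. Pre-specify baseline PSQI in the SAP as a covariate for the subjective sleep outcomes. For the EEG outcomes, use the first night's 0.5-2 Hz power recorded before the first train; the design already collects it.
4. Label any treatment-by-baseline term as exploratory. With about 30 subjects it is too imprecise to carry a statement about disturbed sleepers.

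The cost is a narrower claim, a short SAP addition and one 10-question form per subject. Eligibility and sample size need not change.

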In this branch of our study we will test older adults' response to tACS applied during NREM sleep, with addition of frequency nesting in multiple frequencies which recapitulate intrinsic sleep EEG signals. Nested tACS will be applied in-phase in reference to underlying EEG signal using closed-loop stimulation. Our outcomes will include EEG data, cognitive performance, and assessment of sleep quality. This will be a randomized-controlled cross-over trial with two study arms: a tACS treatment group nesting, , and a sham treatment group. Additionally, prior to the two treatment arms, subjects will undergo an adaptation night which gives them the chance to practice using and sleeping with the equipment. There will be no tACS during the adaptation night but EEG will be recorded. Subjects can begin the treatment arms between three days and three weeks after completing the adaptation night.

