This will be a randomized-controlled trial with two study arms: a tACS treatment phase and a sham treatment phase. The subjects will be assigned to one of two treatment groups (tACS vs sham) in a 1:1 ratio using block randomization. Stimulation will be applied in-phase, single frequency or nested, if indicated based on the results of experiments 1 and 2. Computer-generated randomization will place each subject into one of the study groups. The primary outcome measured is EEG power of slow wave sleep of 0.5-2 Hz, measured immediately before and after each train of stimulation. To detect a significant change ($p<0.05$) of EEG power increase $\geq 20\%$ above sham, with a power of 0.80, a sample size of 30 subjects will be necessary. Subjects will receive either stimulation type, tACS or sham, each night for the one week study period, for up to 7 stimulation sessions pending results of Experiment 2. Subjects will have up to 24 weeks to complete all study sessions and complete the trial. The proposed study seeks to enroll 35 participants to account for participants that may fail our screening criteria, have unusable data or drop-out of the study before completion.

Secondary outcomes will include analysis of slow wave EEG coherence, slow and fast spindle activity, duration of slow wave sleep, total duration of sleep, and subjective sleep quality reported on the Consensus Sleep Diary (CSD), Pittsburgh Sleep Quality Index (PSQI), mood assessment by the Hospital Anxiety and Depression Scale (HADS), overall function in the Clinical Global Impression of Change (CGIC).

Consensus Sleep Diary (CSD)

The CSD is a sleep journal instrument that is designed to measure sleep and has been validated for intervention trials in insomnia (38, 41).

Word Paired-Associate Task

Our computerized paired-associate task consists of 48 semantically related words selected from a normative database with assessment of memory encoding on recollection performance (25, 42)

Finger Tapping Task

This is a finger sequence tapping task of procedural memory. Subjects repeatedly finger-tap with their non-dominant hand a five-element sequence presented on a computer monitor, e.g. 4-2-3-1-4, as fast and accurately as possible on a key board (7).

Pittsburgh Sleep Quality Index (PSQI)

This is a 10 question questionnaire consisting of questions related to usual sleep habits (39).

The Hospital Anxiety and Depression Scale (HADS)

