Total time		60 minutes

HOME PORTION- ADAPTATION NIGHT

Name of Instrument/tool/procedure	Purpose (i.e. what data is being collected)	Time to complete
EEG Recording	Gather EEG data before and after stimulation	overnight
Complete Consensus Sleep Diary	Assess Sleep Quality (after each night of study)	10 minutes
Total time		Overnight

HOME PORTIONS-tACS TREATMENT NIGHTS

Name of Instrument/tool/procedure	Purpose (i.e. what data is being collected)	Time to complete
tACS/EEG Stimulation and Recording	Gather EEG data before and after stimulation	overnight
Complete Consensus Sleep Diary	Assess Sleep Quality (after each night of study)	10 minutes
Word Paired-Associate Task	Assess Memory Encoding (before and after sleep)	20 minutes
Finger Tapping Task	Assess Procedural Memory (before and after sleep)	15 minutes
Total time		Overnight x 3 nights (1 week apart for washout)

VISITS TWO, FOUR, and SIX

Name of Instrument/tool/procedure	Purpose (i.e. what data is being collected)	Time to complete
Post-procedure questionnaire	Assess for tolerability of device and address any safety concerns	15 minutes
Collection of Sleep Diary and Equipment	Collect and Inventory Instruments and Hardware	15 minutes
Total time		30 minutes

VISITS THREE, and FIVE

Name of Instrument/tool/procedure	Purpose (i.e. what data is being collected)	Time to complete
EEG/tACS Equipment Distribution	Ensure subjects remember proper equipment use	20 minutes
Total time		20 minutes

5. tACS SLEEP MODULATION MCI EXPERIMENT

INITIAL VISIT

Name of Instrument/tool/procedure	Purpose (i.e. what data is being collected)	Time to complete
Gather informed consent/UBACC	Gather consent/Screen for capacity	15 minutes
EEG/tACS Equipment Trial	Teach subjects proper equipment use/adjust for comfort	45 minutes
HADS	Assess anxiety and depression (to be administered for MCI trial)	5 minutes
CGIC	Assess Global Impression (to be administered for MCI trial)	5 minutes
Total time		60-70 minutes

HOME PORTIONS

Name of Instrument/tool/procedure	Purpose (i.e. what data is being collected)	Time to complete
tDCS/EEG Stimulation and Recording	Gather EEG data before and after stimulation	overnight
Complete Consensus Sleep Diary	Assess Sleep Quality (after each night of study)	10 minutes

Word Paired-Associate Task	Assess Memory Encoding (before and after sleep each night)	20 minutes
Finger Tapping Task	Assess Procedural Memory (before and after sleep)	15 minutes
Total time		Overnight x 7 nights

VISITS TWO, FOUR and SIX

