All efforts will be made to protect the confidentiality of research subjects. All electronic data will be collected via REDCap, de-identified by the research team, and stored on their servers. Only study personnel will have access to the data. The dataset will be stored on a computer that is password-protected, virus-protected, and automatically logs the user off after a period of inactivity. The computer is located in a locked office. The computer will be password protected when not in use. All written data will be stored in a locked file cabinet in a private office, the research office of the Department of Neurology. All personnel involved in the study have completed HIPAA training. Any PHI will be stripped from data files (or shredded from written records) within 6 months of the end of the data collection period such that all PHI will be deleted prior to completion of the final data set. Any publication of data will be reported in aggregate.

XV. WITHDRAWAL OF PARTICIPANTS

Subjects will be withdrawn if they experience adverse effects due to tACS application or are unable to tolerate wearing of equipment. Data from subjects that withdraw will be collected and protected, but not utilized in the data analysis. Follow up will only be performed in the case of adverse events to ensure the safety of the patient.

XVI. RISKS TO PARTICIPANTS

tACS

Over 10,000 research subjects had received tES, including tACS, as of 2014, without any serious side effects reported (51). There has been no evidence of seizures, neuronal pathology, edema or neuropsychological damage (15). At-home, unsupervised, application of tES has been demonstrated to be safe and well-tolerated, without any major adverse events or safety concerns (26, 27). During administration of tES, subjects have reported a mild tingling sensation (70.6%), moderate subjective fatigue (35.3%) and a light itching sensation (30.4%). After administration of tES, subjects have reported mild transient headaches (11.8%), nausea (2.9%) and insomnia (0.98%) (52). Our stimulation parameters (maximum current density 0.515 mA/cm²) are far below established safety thresholds of 14.29 mA/cm² (49). All stimulation parameters within this proposal are well below currently accepted safety guidelines for tACS (50).

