Official Title: Application of Transcranial Alternating Current Stimulation for Modulation of Sleep and Cognitive Performance

NCT03112902

June 6th, 2021

Statistical Analysis Plan: For each arm, we will perform a three-arm cross-over design to determine whether there is a significant group difference between each tES condition as measured in EEG power in 0.5-2 Hz frequency following tES using repeated measures ANOVA. Recruitment of 15 subjects, with cross-over intervention (*sample size* 15) will allow us to detect differences between groups with an effect size of Cohen's  $d = 1.2$ , power of 80%, and significance of 0.05. This is based on sample sizes and effect sizes reported with motor network tES. Planned secondary analyses of each arm will include scores of slow wave EEG coherence, slow and fast spindle numbers, total duration of each sleep stage, changes in slow wave coherence, changes in slow wave power, self reported sleep timing changes, changes in anxiety and depression (measured by HADS), changes in clinical global impression of change (CGIC), and cognitive performance data, including assessment of procedural memory, verbal (declarative) memory encoding, attention/working memory/visuospatial processing using repeated measures ANOVA of the data.

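### The MCI branch schedules no untreated night and no pre-treatment diary, so its whole-night sleep and diary secondary outcomes have no baseline

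*Protocol*

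**What the plan says.** **Older adults.** Protocol IV.4 states that before the two treatment conditions "subjects will undergo an adaptation night which gives them the chance to practice using and sleeping with the equipment". It adds: "There will be no tACS during the adaptation night but EEG will be recorded". XII.4 gives this night its own table, "HOME PORTION- ADAPTATION NIGHT", which lists overnight EEG and the Consensus Sleep Diary.

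**MCI.** IV.5 describes a 1:1 randomised comparison of tACS with sham: "Subjects will receive either stimulation type, tACS or sham, each night for the one week study period, for up to 7 stimulation sessions". XII.5 has an initial visit (consent and capacity screen, a 45-minute equipment trial, HADS, CGIC) and then one block of home nights, "Overnight x 7 nights". There is no adaptation table. The diary is filled in after study nights only. IV.5 lists slow wave sleep duration, total sleep, the diary and the PSQI among the secondary outcomes.

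**Withdrawal.** Under XV, subjects who "are unable to tolerate wearing of equipment" are withdrawn, and the data of withdrawn subjects are left out of the analysis.

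**SAP.** The secondary analyses include the duration of each sleep stage and "self reported sleep timing changes". The SAP describes a three-arm cross-over for every arm and gives no separate analysis for a parallel MCI comparison.

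**The concern.** The protocol decided that older adults should sleep in the equipment once before treatment. It gives no reason for leaving this out for MCI subjects, who also need a study partner to apply the equipment. As IV.5 reads, MCI is the only randomised branch without cross-over. In the cross-over branches each subject contributes a sham night as their own control. In the MCI branch a whole-night outcome is compared between different people aged 45 to 90, with all of the between-person variation left in.

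Aims 4 and 5 concern sleep architecture and sleep quality in MCI, so these secondary outcomes matter for the branch. Without an untreated value, a change in total sleep, stage duration or diary report cannot be computed, and no baseline covariate is available to reduce the noise.

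**Working it through.** **1. Is there an untreated MCI night anywhere?** The payment caps in IX serve as a cross-check at $25 per home visit.

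- MCI: $175 / $25 = 7 nights. XII.5 also gives 7, and IV.5 makes each one tACS or sham, so untreated nights = 7 − 7 = 0.
- Older adults: $75 / $25 = 3 nights = 1 adaptation + 2 treatment sessions (IV.4). The XII.4 table lists three treatment nights, which does not match IV.4, but the adaptation night is tabulated separately either way.

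**2. Which MCI outcomes lack a pre-treatment value?** Section XII starts stimulation only in stable stage 2 or deeper NREM sleep, with EEG recorded beforehand.

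| MCI outcome | Earliest scheduled value | Untreated? |
|---|---|---|
| 0.5–2 Hz power (primary) | EEG before the first train, night 1 | Yes |
| Coherence, spindles | Available from the same EEG window | Yes |
| HADS, CGIC | Initial visit | Yes |
| Word-pair and finger-tapping tasks | Before sleep, night 1 | Yes |
| Total sleep, stage duration | Whole of night 1 | No |
| Consensus Sleep Diary | After night 1 | No |
| PSQI | Listed in IV.5, not scheduled in XII.5 | None scheduled |

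The gap is therefore the whole-night durations and the diary. The short window before a train cannot supply a whole-night value.

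**3. The plan's own sample size.** IV.5 states 30 subjects for an increase of at least 20% above sham, at p<0.05 and power 0.80. This cannot be reproduced, because no standard deviation is given. Solving backwards for 15 per arm (two-sided 5% assumed, since sidedness is not stated):

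- Normal approximation: d = (1.960 + 0.842) × √(2/15) = 1.02, an implied SD of 20/1.02 ≈ 19.6 points.
- Noncentral t, 28 degrees of freedom: d = 1.06, an implied SD of 20/1.06 ≈ 18.9 points.

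That figure was set for the primary outcome. It is used below only to fix 15 per arm.

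**4. What a baseline could be worth.** With a baseline correlated r with the outcome, the residual variance is multiplied by 1 − r². The detectable difference becomes 1.06 × √(1 − r²), and the effective sample size is multiplied by 1/(1 − r²). The documents give no r, so the range is assumed. The one degree of freedom spent on the covariate is ignored.

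| r (assumed) | 1 − r² | Detectable d | Effective n | Power at an assumed d = 0.8 |
|---|---|---|---|---|
| No baseline | 1.00 | 1.06 | × 1.00 | 56.2% |
| 0.3 | 0.91 | 1.01 | × 1.10 | 60.2% |
| 0.5 | 0.75 | 0.92 | × 1.33 | 68.5% |
| 0.7 | 0.51 | 0.76 | × 1.96 | 84.2% |
| 0.8 | 0.36 | 0.64 | × 2.78 | 94.1% |

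At r = 0.3 the gain is small. From 0.5 upwards it is worth having.

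**The case against.** **The branches differ for a defensible reason.** Older adults have one night per condition, so a first-night effect could fall on a whole condition. MCI subjects have up to seven nights of one condition. Night 1 is one of several, should affect both arms alike, and can be modelled. This stands: the difference between branches is not in itself an error.

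**The illustration is soft.** Every correlation is assumed. The proposed covariate night would also be the subject's first in the equipment, which may pull the correlation down. This stands, and it is why the range includes 0.3.

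**The design is not fully settled.** IV.5 speaks of treatment and sham phases, XII.5 runs to six visits like the cross-over branches, and the SAP says cross-over throughout. The 1:1 allocation and one condition per subject for the week make the parallel reading much the more likely. If the branch were a cross-over, subjects would serve as their own controls and most of the precision argument would fall away.

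**Stronger readings that the documents do not support.**

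- A reader might infer that the MCI comparison is biased. A missing baseline does not bias a 1:1 randomised contrast. Excluding withdrawn subjects (XV) could, but that is a separate matter. Sham subjects wear the same electrodes, so intolerance of wearing them has no obvious reason to differ by arm. The equipment trial and the cap-comfort check in XVI give some screening beforehand.
- A reader might infer that the primary outcome, coherence and spindles also lack a baseline. The pre-train EEG on night 1 supplies one.
- A reader might compare the enrolment allowances, 5 of 35 (14%) for MCI with 20 of 35 (57%) for older adults, and credit or blame the run-in. The healthy 18–50 branch has no run-in and allows 15 of 30 (50%). These allowances also pool screen failures, unusable data and drop-out, so they say nothing about run-ins.

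**Conclusion.** The point holds as a cheap improvement to some MCI secondary outcomes: total sleep time, sleep-stage duration and the Consensus Sleep Diary. None of these has a scheduled untreated value, and the SAP's "self reported sleep timing changes" cannot be computed from the diary in this branch. The SAP does not name the instrument for that outcome; the PSQI might have helped, but XII.5 does not schedule it.

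The size cannot be derived from the documents. On the assumed correlations of 0.5 to 0.8, a baseline would lower the detectable difference from 1.06 to between 0.92 and 0.64. This rests on a parallel design, 15 evaluable subjects per arm and a two-sided 5% test.

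The time of randomisation is not stated. That overnight intolerance of the equipment emerges only after allocation is therefore an inference, though a firm one, since night 1 is already tACS or sham. No intolerance rate is given, so this part has no figure.

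**What to change.** **(a) At minimum.** State an interval between the MCI initial visit and the first session; the protocol sets none now. Have subjects complete the existing sleep diary on those mornings, and name that value in the SAP as the baseline covariate for diary outcomes. Cost: about 10 minutes per morning (the XII.5 figure).

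**(b) Preferably.** Extend the IV.4 adaptation night (EEG and diary, no tACS) to the MCI branch and randomise after it is completed, so that overnight intolerance is found before allocation. Use its whole-night values as the covariate for total sleep and stage duration. Cost: a protocol amendment, one more home night for subject and partner, and up to 35 × $25 = $875 in payments. Extra visits to collect and reissue equipment may be needed; XII.4 lists these at 30 and 20 minutes. Subjects who fail the run-in still count against the 35 enrolled, so it adds no evaluable subjects by itself.

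**(c) With either.** Reconcile the SAP's cross-over wording with the parallel MCI design in IV.5, and schedule the PSQI in XII.5 or remove it from the MCI outcomes.
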